**10.4. Laboratory Evaluations**

Laboratory safety parameters will be analyzed by a central laboratory using standard validated methods.

All laboratory safety data will be collected as per the schedule of assessments.

The following continuous laboratory parameters will be analyzed:

1. Hematology: hemoglobin, hematocrit, erythrocytes, erythrocyte mean corpuscular volume, leukocytes, neutrophils, lymphocytes, monocytes, eosinophils, basophils and platelets
2. Blood Biochemistry: albumin (ALB), alkaline phosphatase (AP), alanine aminotransferase (ALT; SGPT), aspartate aminotransferase (AST; SGOT), blood urea nitrogen (BUN), calcium (Ca), carbon dioxide (CO2), chloride (Cl), creatinine, creatine kinase, gamma-glutamyl transferase (GGT), globulin, glucose, lactate dehydrogenase (LDH), phosphorus, potassium (K), sodium (Na), thyroid function, thyroid stimulating hormone (TSH), total bilirubin, direct bilirubin, total cholesterol, total protein, triglycerides, uric acid.
3. Tests of growth and precocious puberty: Growth hormone (GH), insulin-like growth factor-1 (IGF-1, low sensitivity), prolactin, Luteinizing Hormone (LH), Follicle Stimulating Hormone (FSH), testosterone, estradiol
4. Coagulation: Prothrombin time (PT)/International normalized ratio (INR), activated partial thromboplastin time (PTT)
5. Whole blood cannabidiol
6. Urinalysis: analysis for pH, glucose, ketones, nitrite, protein, bilirubin, urobilinogen, leukocyte esterase, and occult blood. Microscopic analysis will be performed for blood, all cell types, and casts.
7. Urine pregnancy test: Urine pregnancy testing will be performed in female subjects of childbearing potential.
8. Urine THC panel

This document is confidential.

## Statistical Analysis Plan

Sponsor: Zogenix International Limited; Protocol No.: ZX008 Study 2 (ZX008-1501 and ZX008-1502)

---

Observed continuous laboratory data will be descriptively summarized by type of laboratory test/parameter by treatment group. Changes from baseline will also be presented for all continuous laboratory parameters by treatment group over time.

Categorical laboratory parameters will be summarized by presenting the number and % of subjects by visit and by treatment arm.

All laboratory values (including invalid values, reference ranges, and possible flags (low, high,)) will be presented in the subject data listings.

A listing of subjects with Potentially Clinically Significant (Extreme) laboratory results will be provided.

A listing of subjects with markedly extreme abnormal laboratory results will be provided, and additional explorations of the data may be conducted as warranted. Additionally, summaries of abnormal lab results by parameter will be provided to investigate changes in platelet count and prolactin in greater detail. The summaries include:

- Subjects with decrease ( $\geq 25\%$  from baseline) in Platelets count with normal platelet count at baseline
- Subjects with decrease ( $\geq 25\%$  from baseline) in Platelets count relative to baseline (whether normal or abnormal) platelet count
- Subjects with increase ( $\geq 25\%$  from baseline) in prolactin with normal baseline
- Subjects with increase ( $\geq 25\%$  from baseline) in prolactin with normal baseline, and had seizure event within 48 hours prior to prolactin

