#### **10.10. Tanner Staging**

Tanner Staging will be assessed for subjects >7 years old during the study at baseline period (Visit 3) and End of study (Visit 12). Conceptually, pubertal maturation can be described in terms of sequence, timing, and tempo. Puberty consists of a series of predictable events, and the sequence of changes in secondary sexual characteristics has been categorized by several groups. The onset and progress of pubertal changes will be recorded on a 5 point scale for boys and girls separately. Boys are rated for genital development and pubic hair growth through stage I to stage V. Girls are rated for breast development and pubic hair growth through stage I to stage V.

The number and percentage of subjects in each Tanner Stage will be presented for all visits by treatment group separately for boys and girls overall and also broken out for the following age groups:

- >7 years to <=11,
- >11 years to <=15,

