Table	14.3.4.4.1a	Laboratory Parameters – Urinalysis (Quantitative Parameters) (Japan) – Safety Population
Table	14.3.4.4.1b	Laboratory Parameters – Urinalysis (Quantitative Parameters) (Non-Japan) – Safety Population
Table	14.3.4.4.2	Laboratory Parameters – Urinalysis (Categorical Parameters) – Safety Population
Table	14.3.4.4.2a	Laboratory Parameters – Urinalysis (Categorical Parameters) (Japan) – Safety Population
Table	14.3.4.4.2b	Laboratory Parameters – Urinalysis (Categorical Parameters) (Non-Japan) – Safety Population
Table	14.3.4.5	Laboratory Parameters – Tests Of Growth And Precocious Puberty – Safety Population

This document is confidential.

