## 2.4 Study Population

Male and female subjects, aged 2 to 18 years of age with a medical history and clinical diagnosis of Dravet syndrome who meet other eligibility criteria could be enrolled in the study. This section includes the inclusion and exclusion criteria related to cardiac safety.

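### The planned summaries of LH, FSH, testosterone, estradiol and the other growth and puberty tests pool boys and girls aged 2 to 18 within each arm, so a rise confined to pre-pubertal children is diluted at group level

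*SAP*

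**What the plan says.** Section 10.4 (Laboratory Evaluations) of the Study 2 SAP defines one panel as "Tests of growth and precocious puberty: Growth hormone (GH), insulin-like growth factor-1 (IGF-1, low sensitivity), prolactin", followed by "Luteinizing Hormone (LH), Follicle Stimulating Hormone (FSH), testosterone, estradiol". Like every other continuous laboratory parameter, these tests are to be shown as follows: "Observed continuous laboratory data will be descriptively summarized by type of laboratory test/parameter by treatment group". For change the rule is: "Changes from baseline will also be presented for all continuous laboratory parameters by treatment group over time". Neither sentence mentions sex, age or pubertal stage. The population, as described in Section 2.4 of the cardiovascular SAP, is "Male and female subjects, aged 2 to 18 years of age".

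The index in Section 15 lists one main table, 14.3.4.5, titled "Laboratory Parameters – Tests Of Growth And Precocious Puberty – Safety Population", with a Japan version (a) and a Non-Japan version (b). It lists no version by sex, age or Tanner stage. The Study 1 SAP (Section 6.4.9 and Appendix 1) has the same grouping rule and a single pooled table.

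Tanner stage is treated differently. Section 10.10 presents it "by treatment group separately for boys and girls overall and also broken out for the following age groups", but only for subjects older than 7 years.

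**The concern.** Testosterone and estradiol differ between boys and girls, and most of this panel changes with puberty. In an arm spanning ages 2 to 18, the pubertal subjects dominate the mean and its spread. A rise in the youngest children, for whom early puberty is the question, adds little to either.

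The plan splits Tanner stage by sex and age band but does not split the hormones that bear on the same question. Because Tanner staging starts above age 7, these hormones are the only planned pubertal measure in younger children, and there the summary is coarsest. The split is also accepted elsewhere: the Study 2 cardiovascular SAP tabulates ECG intervals by age band (QTcF also by sex), and Section 10.3 commits adverse events by age and sex.

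At stake is whether a group-level hormone signal in young children would be visible in a committed table, or would depend on someone finding it in a listing.

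**Working it through.** The plan states no figure on this point. The check has two parts: what the plan commits to, and how strongly pooling dilutes a signal.

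**Outputs that could show a rise in young children (Study 2 SAP)**
- Table 14.3.4.5: by arm only, plus Japan and Non-Japan.
- Section 6.7: selected safety outputs may be split by age (under 6, 6 and over) and sex, but none is named. Section 6.1.3 of the Study 1 SAP offers age only.
- Extra abnormality counts in Section 10.4: platelets and prolactin only.
- Extreme-value and most-abnormal listings in the index: no hormone version.
- Listing 16.2.8.5, "Tests Of Growth And Precocious Puberty": individual values, with reference ranges and low/high flags under Section 10.4.
- Adverse events by age and by sex (Section 10.3): these include laboratory findings judged clinically significant.

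**Dilution, observed values**

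From the documents: 40 per arm (Section 2.5) and at least 25% under 6 (Section 12), so 10 per arm.

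Assumed: half the arm is pubertal, with levels R = 5, 10 or 20 times a pre-pubertal mean of 1; within-group CV is 60%; the hormone doubles in the 10 youngest of one arm.

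- Pooled mean: 0.5 + 0.5R = 3.0, 5.5, 10.5.
- Shift: 0.25 × 1 = 0.25, which is 8.3%, 4.5% and 2.4% of the mean.
- Standard error (SE) of the arm difference when the pubertal share varies by chance. Variance = 0.5(1.36) + 0.5(1.36R²) − mean² = 8.68, 38.43, 162.43. SE = √(2 × variance/40) = 0.66, 1.39, 2.85. The shift is 0.38, 0.18 and 0.09 SE.
- SE with exactly 20 pubertal subjects per arm. Within-group variance is 0.18 + 0.18R² in the control arm and 0.45 + 0.18R² in the other. SE = √((0.63 + 0.36R²)/40) = 0.49, 0.96, 1.90. The shift is 0.51, 0.26 and 0.13 SE.
- Under-6 group alone: SE = √((1.2² + 0.6²)/10) = 0.42, so the rise of 1 is 2.4 SE. Split by sex as well (about 5 per cell): 1/√(1.8/5) = 1.7 SE.

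The planned statistics also include the median and quartiles (Section 6.1). Simulating the same scenario with lognormal values and exactly 20 pubertal subjects per arm, the lower quartile rises by about 40 to 42%, or about 1.5 SE of the arm difference, for all three values of R.

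**Dilution, change from baseline**

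Assumed: a rise of 2 pre-pubertal SDs in a fraction f = 0.25 of one arm, with pubertal SD of change equal to k times the pre-pubertal SD. The mean shift is 0.25 × 2 = 0.50. Variance is 0.25 + 0.75k² in the control arm, plus 0.25 × 0.75 × 2² = 0.75 in the other.

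| k | SE of difference | Shift in SEs |
|---|---|---|
| 1 | 0.26 | 1.91 |
| 5 | 0.98 | 0.51 |
| 10 | 1.94 | 0.26 |
| 20 | 3.88 | 0.13 |

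In the pre-pubertal stratum (10 per arm) the figure is 2/√(2/10) = 4.47, and within one sex (about 5 per arm) 2/√(2/5) = 3.16.

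In a simulation of the doubling scenario with an assumed within-child log correlation of 0.5 to 0.8, the mean change moves by 0.1 to 0.8 SE and the median change by about 1.0 to 1.4 SE.

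**The case against.** A reader might infer that a rise in pre-pubertal children could not be seen at all. The documents do not support that. Every value is listed with its range and flag, and Listing 16.2.8.5 is dedicated to these tests. Change from baseline is summarised, which removes each child's starting level. Medians and quartiles are planned, and the lower quartile responds noticeably even in the scenario above. Clinically significant laboratory findings count as adverse events, and in Study 2 these are committed by age and sex (Table 14.3.1.16 is indexed for age). Section 10.4 also allows further exploration of the data.

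A reader might also take detection of precocious puberty to be a stated objective. It is only the heading of a test panel; the safety objective names laboratory parameters in general. Nor is a misleading arm difference from a chance imbalance in pubertal subjects a strong argument. It applies mainly to observed means, is reduced by change from baseline, and concerns a descriptive table.

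These points remove any claim of invisibility but not the gap itself. A listing gives no comparison between arms. The adverse event route depends on an investigator judging the value significant, and the Study 1 SAP has no adverse event tables by age or sex. The subgroup output is optional and unnamed. Splitting by both sex and age also has a price: at about 5 per cell, 1.7 SE is close to what the pooled lower quartile already shows.

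**Conclusion.** The point holds as one of dilution. The committed hormone summaries pool sex and age within each arm, and no other committed output compares the arms on hormone levels in young children. Under the stated assumptions, a doubling in the under-6s moves the pooled observed mean by about 0.1 to 0.5 SE and the lower quartile by about 1.5 SE, against about 2.4 SE within the under-6 group and about 1.7 SE within one sex of it.

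These sizes are illustrations. The hormone ratios, the CV and the pubertal share are not in the documents, and the dilution is mild if pubertal and pre-pubertal variability are similar (1.91 against 4.47 for change from baseline at k = 1). The 1.5 SE for the lower quartile also assumes the same pubertal share in both arms; chance variation in that share would reduce it.

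This is not a contradiction or an error in the plan. It is a poorly suited grouping for a paediatric safety table, worth changing because the change is cheap.

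**What to change.** Commit Table 14.3.4.5 in the Study 2 SAP, and its Study 1 equivalent, by sex and by the existing age strata (under 6, 6 and over), for both observed values and change from baseline. Keep the pooled version alongside.

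Add counts, by arm and sex, of subjects who move from within to above their reference range between baseline and any visit in the T+M period. The ranges and flags are already held for the listings. State that the ranges used are specific to age and sex; otherwise the counts would repeat the pooling problem.

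The cost is SAP wording and extra rows in one table, with no new data and no testing. Cells will be small (about 5 per arm where sex is crossed with age under 6), so the results should be labelled descriptive.

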### 10.5. Vital Signs

Vital signs data including blood pressure, heart rate, temperature, respiratory rate, weight, and BMI will be documented for subjects during study at screening visit (visit 1), randomization (visit 3) prior to first dose of study medication, titration period (visit 6), and maintenance period (visit 8 and visit 10) and at EOS visit (visit 12).

The mean value and change from baseline to each on-study evaluation will be summarized for vital signs and weight by treatment group. Vital signs, Weight and BMI data will be presented for each patient in a data listing.

For each subject with a clinically meaningful abnormality in vital signs, weight, or BMI (to be supplied by Sponsor), a table will be produced organized by parameter that lists each subject, age, sex, day of most abnormal value, the most abnormal value, and the reference range.

A listing of each subject's values will be created.

### 10.6. ECG

12-Lead ECGs data (PR, QRS, QT, QTcF, and HR) will be documented for subjects during study at baseline (Visit 1 and Visit 3), Day 43 (Visit 8), at End of Study (Visit 12) and at Cardiac Follow-up (Visit 14).

Analysis of Echocardiograms will be included in a separate report from ERT.

This document is confidential.

All ECG values will be presented in the subject data listing. In addition to the subject data listing with all ECG values, a listing of all abnormal, clinically relevant findings will be presented organized by subject, by parameter, then by visit.

#### **10.7. Doppler Echocardiography**

Color Doppler echocardiography (ECHO) will be conducted at a facility with experience for the subject's age at Screening, Maintenance period (Visit 8), End of study (Visit 12), and Cardiac Follow-up (Visit 14). ECHO uses ultrasound technology to examine the heart or blood vessels. An ECHO uses high frequency sound waves to create an image of the heart while the use of Doppler technology allows determination of the speed and direction of blood flow by utilizing the Doppler effect. Predetermined standard guidelines on the proper evaluation of certain measurements, as well as abnormality thresholds, were constructed by the sponsor's IPCAB prior to study initiation. These thresholds are provided in Cardiovascular SAP.

Results of ECHOs will be presented in a separate report from ERT.

#### **10.8. Physical Examination**

A complete physical examination will be performed at Screening Visit (Visit 1), day of randomization (visit 3) prior to first dose of study medication, and at the EOS visit. An abbreviated physical exam is performed at Day 15 (Visit 6), 43 (Visit 8), and 71 (Visit 10). A complete or abbreviated physical exam may be performed at the Cardiac follow-up visit for patients who do not enter the open-label extension study if clinically warranted.

All physical examination results will be presented in a subject data listing, including the description of abnormalities. New, clinically meaningful abnormalities will be reported as adverse events.

#### **10.9. Neurological Examination**

A complete neurological examination will be performed at Screening Visit (Visit 1) and EOS (Visit 13). An abbreviated neurological examination will be performed at randomization (visit 3) and at Visit 6.

Shift tables representing neurological exam results from randomization to EOS will be presented by body system.

All neurological examination results will be presented in a subject data listing, including the description of abnormalities.

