**6.4.4 Neurological Examination**

A complete neurological examination will be performed at Screening Visit (Visit 1) and EOS (Visit 13). An abbreviated neurological examination will be performed at randomization (visit 3) and at Visit 6.

Shift tables representing neurological exam results from randomization to EOS will be presented by body system.

All neurological examination results will be presented in a subject data listing, including the description of abnormalities.

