**6.4.5 Vital Signs, Weight, and BMI**

Vital signs data including blood pressure, heart rate, temperature, respiratory rate, weight, and BMI will be documented for subjects during study at screening visit (visit 1), randomization (visit 3) prior to first dose of study medication, titration period (visit 6), and maintenance period (visit 8 and visit 10) and at EOS visit (visit 12).

The mean value and change from baseline to each on-study evaluation will be summarized for vital signs and weight by treatment group. Vital signs, Weight and BMI data will be presented for each patient in a data listing.

For each subject with a clinically meaningful abnormality in vital signs, weight, or BMI (to be supplied by Sponsor), a table will be produced organized by parameter that lists each subject, age, sex, day of most abnormal value, the most abnormal value, and the reference range.

A listing of each subject’s values will be created.

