**Statistical Analysis Plan**

Sponsor: Zogenix International Limited; Protocol No.: ZX008 Study 2 (ZX008-1501 and ZX008-1502)

Table 4: Schedule of Assessments

Study Assessments	Baseline Period a			Titration + Maintenance Period								EOS/ ET b	Post- Dosing	Cardiac Follow-up
	Screening	2	Random- ization	Titration Period			Maintenance Period							
	1	(Phone)	3	4, 5 (Phone)	6	7 (Phone)	8	9 (Phone)	10	11 (Phone)	12			
Visit Number	1	2 (Phone)	3	4, 5 (Phone)	6	7 (Phone)	8	9 (Phone)	10	11 (Phone)	12	13	14	
Study Day	-42 to -41	-21	-1	1	4, 8	15	29	43	57	71	85	99	113	3-24 mo post dose
Informed Consent (subject and parent)	X													
Inclusion/Exclusion Criteria	X		X											
Demographics	X													
Medical/Neurological History	X													
Epilepsy history	X													
Collect retrospective seizure diary data	X													
Prior Medication	X		X											
Physical Examination, complete	X		X						X			X		X c
Physical Examination, abbreviated					X			X		X				X c
Neurological Examination, complete	X										X			
Neurological Examination, abbreviated			X		X						X			
Vital signs	X		X		X			X		X		X		
Weight, Height, BMI	X		X		X			X		X		X		
12-lead ECG	X		X		X			X		X		X		X c
Doppler ECHO		X						X c				X c		X c
Urine pregnancy test	X c		X c		X c			X c		X c		X c		
Clinical laboratory evaluation (hematology/clinical chemistry/urinalysis, etc)	X		X		X			X		X		X		
Plasma sample for ZX008 pharmacokinetics								4X c						
Plasma sample for background AEDs			X c		X c			X c				X c		
Urine THC Panel/Whole blood CBD	X		X		X			X		X		X		
Janner Staging (for subjects >7 years old)			X		X							X		
Subject Diary	D	R	C/R/D		R	C/R/D	R	C/R/D	R	C/R/D	R	C/R/D d	C/R	
Epilepsy genotype panel	X											X		
Study Medication			D		R e	C/R/D	R	C/R/D	R	C/R/D	R	C/R/D f	C/R	
C-SSRS	X		X			X		X		X		X		

This document is confidential.

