**Statistical Analysis Plan**

Sponsor: Zogenix International Limited; Protocol No.: ZX008 Study 2 (ZX008-1501 and ZX008-1502)

The targeted study day and allowable windows for visits in are reproduced from the protocol below. Early termination visits will be mapped to a visit based on these windows.

Table 5. Time Windows for Assessments

Visit / Procedure	Time window (relative to scheduled visit / procedure)
Visit 1 (Clinic; Study Day -43 to -42 or -42 to -41):	Not applicable
Visit 2 (Phone; Study Day -21)	± 3 days
Visit 3 (Clinic; Study Day -1; Randomization)	+ 4 days a
Visits 4, 5 (Phone: Study Days 4, 8)	± 3 days
Visit 6 (Clinic; Study Day 15)	± 4 days
Visit 7 (Phone: Study Day 29)	± 4 days
Visit 8 (Clinic; Study Day 43)	± 4 days
Visit 9 (Phone: Study Day 57)	± 4 days
Visit 10 (Clinic; Study Day 71)	± 4 days
Visit 11 (Phone: Study Day 85)	± 4 days
Visit 12 (Clinic; Study Day 99)	± 4 days
Visit 13 (Clinic; Study Day 113; post dosing)	± 4 days
Visit 14 (ECHO clinic; 3-6 months after last dose)	+ 30 days
Blood collection for ZX008 PK	± 15 minutes
Blood collection for AED concentration	Prior to morning dose of AED medication

AED=antiepileptic drug (s); ECHO=echocardiogram; PK = pharmacokinetics

a In cases where the screening period is extended beyond 42 days, the immediate 42 days before the Randomization visit will be used to calculate the baseline seizure frequency

This document is confidential.

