#### Other Definitions:

Treatment completers are those subjects that are compliant with IMP at least 85% of dosing days and fulfill at least one of the following criteria:

- Subjects that did not discontinue from the trial prior to end of study visit at Day 99 ± 4 days (Visit 12).
- Subjects that complete the Treatment Period (T+M) starting from Study Day 1 through the protocol defined end of study visit at Day 99 ± 4 days (Visit 12).
- Subjects that enroll in the open label extension study.

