**6.5. Visit Windows**

The following rules will be used to window data into treatment periods for by treatment period tabulations. For all by-visit tabulations, the nominal visit as recorded on the CRF will be used.

Double Blind Treatment Period	
The Double-Blind Treatment Period start date is the date of first treatment, Study Day 1 (ie, the day after V3). The Double-Blind Treatment Period end date is the last date the patient was on study treatment.
 
The Double-Blind Treatment Period consists of 16 weeks from first treatment start date, which includes 2 weeks of Titration period, 12 weeks of Maintenance period and 2 weeks of Taper/Transition period; therefore the end date would be considered the date at Visit 13.
 
For subjects who discontinue early from the study, the double-blind treatment period end date will be the date at the early termination visit (Visit 12).

Titration Period	
The Titration Period covers the first 14 ± 4 days of treatment while subjects are titrated to their randomized dose. It begins on the first day of treatment (Study Day 1) and extends through Visit 6 (when the patient has reached their randomization dose). The Titration Period applies to all subjects including placebo recipients. If a subject withdraws from the study prior to treatment in the maintenance period, all safety assessments and events up to and including the date of study withdrawal will be tabulated in the titration period.

Maintenance Period	
The Maintenance Period covers the 12 weeks following the end of the titration period. It begins on the date of Visit 6 + 1 day and extends through the end of study/early termination visit (Visit 12).

Titration + Maintenance Period (T+M)	
The T+M period combines the Titration and Maintenance periods, beginning on the date of first treatment (Study Day 1) and extending to the end of study/end of treatment visit. The T+M period is considered the treatment period.

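### The neurological shift table compares an abbreviated exam at randomisation with a complete exam at end of study, and the text gives end of study the wrong visit number

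*SAP*

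**What the plan says.** The neurological sections of the two plans (6.4.4 in the Study 1 SAP, 10.9 in the Study 2 SAP) carry the same text. On the complete exam: "A complete neurological examination will be performed at Screening Visit (Visit 1) and EOS (Visit 13"). On the short one: "An abbreviated neurological examination will be performed at randomization (visit 3) and at Visit 6". The analysis is then one sentence, "Shift tables representing neurological exam results from randomization to EOS will be presented by body system", plus a subject listing of all results with descriptions of abnormalities.

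Other parts of the same documents number the end-of-study visit differently:

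- The vital signs sections (6.4.5 and 10.5) end their visit list with "and at EOS visit (visit 12").
- The treatment-completer definition (6.1.5 in Study 1; Other Definitions under 6.2 in Study 2) reads "Subjects that did not discontinue from the trial prior to end of study visit at Day 99 ± 4 days (Visit 12").
- The Maintenance Period in the visit-window sections (6.1.6 and 6.5) "extends through the end of study/early termination visit (Visit 12").
- The time-window table of the Study 2 SAP (Table 5, section 2.8) describes "Visit 13 (Clinic; Study Day 113; post dosing").

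**The concern.** There are two separate faults.

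The first is the visit number. Visit 13 comes after the taper or transition, so an exam there would not be made on the randomised dose, and none is scheduled.

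The second remains once the number is corrected. The table starts from an abbreviated exam and ends at a complete one, broken down by body system. If a system is examined less thoroughly at Visit 3 than at EOS, a deficit present from the outset can be recorded as normal at the start and abnormal at the end. If a system is not examined at all at Visit 3, the section does not say what starting value applies. A matched pair of complete exams already exists, at Screening and at EOS, and the table does not use it.

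Neurological examination is a named safety item (Study 1 SAP section 2.4; Study 2 SAP sections 2.2 and 4.2). The Study 1 introduction describes ataxia and psychomotor regression as part of the disease, so abnormal findings at entry are to be expected. The shift table is the only planned summary of these data.

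**Working it through.** The plan states no figure on this point, so the check sets the sections side by side and adds some day arithmetic.

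**1. Which visit is EOS?** The completer definition, the period windows and the vital signs sections all give Visit 12. So do the sections on ECG (6.4.6, 10.6), Tanner staging (6.4.8, 10.10), C-SSRS (6.4.10, 10.11) and BRIEF (6.4.11, 10.12). Only the neurological sections say Visit 13.

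**2. Is there a neurological exam at Visit 13?**

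- Study 1 SAP, Table 1: the row "Neurological Examination, complete" is marked at Visits 1 and 12. The abbreviated row is marked at Visits 3 and 6.
- Study 2 SAP, Table 4: the complete row has two marks, one at Visit 1 and one under Visit 12 by the table's visit-number row. In the copy at hand the study-day row is offset by one column from the visit-number row; read by study day, the second mark would fall under Day 85, a phone visit. On neither reading does it fall under Visit 13.
- The abbreviated row of Table 4 has marks at Visits 3 and 6 and a third in the same column as the complete end-of-study exam.

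**3. What would a Visit 13 exam reflect?**

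- Gap between visits: 113 − 99 = 14 days.
- Taper: 8 days, Days 100 to 107, so tapering subjects would be 113 − 107 = 6 days past the last taper day.
- Transition, step 2 (days 5 to 14 after Visit 12): 99 + 5 = Day 104 to 99 + 14 = Day 113. The transition tables put all three arms on the same dose in this step.

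A Visit 13 exam would therefore not describe subjects on their randomised treatment.

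**4. Which exams form a matched pair?**

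| Visit | Exam type (6.4.4 and 10.9) |
|---|---|
| 1, Screening | complete |
| 3, randomisation | abbreviated |
| 6 | abbreviated |
| EOS | complete |

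Planned comparison: Visit 3 to EOS, abbreviated to complete. Matched comparisons available: Visit 1 to EOS (complete) and Visit 3 to Visit 6 (abbreviated). The physical examination differs: its Visit 3 exam is complete (6.4.3, 10.8), so a randomisation-to-EOS comparison there would be like for like.

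**5. What does moving the start to Screening cost in time?** There is no Day 0. From Day −1 to Day 99 is 1 + 98 = 99 days. From Day −42 to Day 99 is 42 + 98 = 140 days. The interval lengthens by 140 − 99 = 41 days, about six weeks.

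**6. Is the table in the output lists?** Appendix 1 of the Study 1 SAP and section 15 of the Study 2 SAP each contain Listing 16.2.9.6 for the neurological examination and no neurological shift table.

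**The case against.** A reader might infer that the table cannot be filled because nothing is examined at Visit 13. The documents do not support that. The shift sentence says EOS without a visit number, EOS is Visit 12 wherever else it is numbered, and by-visit tabulations use the nominal visit on the CRF (6.1.6, 6.5). In practice the complete exam at Visit 12 would be used, and the visit number is a labelling error.

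A reader might also infer that the mismatch would hide a drug effect or create a calculable number of false abnormalities per arm. That is not supported either. The SAPs give neither the content of the abbreviated exam nor the frequency of abnormalities at entry, so no count can be derived. All arms follow the same exam sequence, so no arm is favoured. Every result is also listed with its description, and a new unfavourable sign falls within the adverse event definition (6.4.1, 10.3).

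The baseline rule is a fair partial defence. Sections 6.1.4 and 6.2 define baseline for other endpoints as the latest non-missing pre-treatment result in the 42-day window, so a system not examined at Visit 3 could take its Screening value. This defence has limits. The shift sentence starts from randomisation and does not cite the rule. Table 5 of the Study 2 SAP allows Screening at Day −43 and Visit 3 up to four days late, so Screening can fall outside the window. And where a system was examined briefly at Visit 3, the brief result is the latest one, so the rule selects it.

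The third abbreviated mark in Table 4 of the Study 2 SAP might suggest a matched exam at EOS. It is weak evidence: section 10.9 lists only Visits 3 and 6, Table 1 of the Study 1 SAP has no such mark, and in the copy at hand the ECG row of Table 4 shows seven marks against the five visits in section 10.6. Even if real, the section does not say which exam would feed the table.

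Finally, a baseline close to first dose is a reasonable preference. That stands as a cost of the change.

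**Conclusion.** The point holds, with modest weight. Sections 6.4.4 and 10.9 give the wrong visit number for EOS, and the planned shift table compares an abbreviated exam with a complete one although a complete-to-complete comparison is available. Some shifts may reflect the exam rather than the subject.

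How many cannot be stated. It depends on what the abbreviated exam leaves out or covers less fully, which the SAPs do not define; if it covered every body system as well as the complete exam does, this part of the problem would disappear. Whatever its size, the effect is noise common to all arms in a descriptive safety display. It does not touch the primary or key secondary analyses. It is worth correcting because the table is the only planned summary of a named safety endpoint, and because its absence from both output indexes means no later specification there resolves the ambiguity.

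**What to change.** In section 6.4.4 of the Study 1 SAP and section 10.9 of the Study 2 SAP:

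- Change the EOS visit number from Visit 13 to Visit 12/ET.
- Build the shift table by randomised arm and body system from the complete exam at Screening (Visit 1) to the complete exam at Visit 12/ET. If a start nearer to first dose is preferred, keep Visit 3 to EOS but restrict it to body systems covered by both exam types, and name those systems.
- If early change is of interest, add a separate abbreviated-to-abbreviated shift from Visit 3 to Visit 6.
- Add the table to Appendix 1 (Study 1) and section 15 (Study 2).

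This takes a sentence or two in each plan and one entry in each index, and needs no new data. The drawback of the Screening start is that the first exam lies about six weeks before first dose, so a change during the untreated baseline period would be counted in the shift. A footnote to the table can say so.
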